We plan to enroll a total of 200 subjects, including 60 early-stage patients (SARA total score 3-9.5), 60 premanifest gene mutation carriers (SARA total score 0-2.5), 60 50%-at-risk subjects (SARA total score 0-2.5), and 20 patients, who had a SARA total score <10 during the previous (2009-2012) natural history study. Confirmatory genotyping for SCA1 and SCA3 will be performed on blood samples obtained at the baseline visit. For 50%-at-risk subjects, genotyping results will be released to the subject's designated physician or genetic counselor after a release of information form has been signed. We strongly recommend genetic counseling for the disclosure of DNA results. We expect that the SCA1-to-SCA3 enrollment ratio will be approximately 1 to 2 in the US and 1 to 1.2 in Europe, based on the previous studies. We anticipate <5%-attrition rate and plan to replace subjects, who drop out, with new subjects. The low attrition rate is expected because study subjects have mild or no disability and low mortality. During the study, there will be individuals who will phenoconvert and some subjects who will want to know the DNA testing results. Subjects who become clinically ataxic will be categorized in the phenoconversion group. Asymptomatic subjects, who receive positive DNA results, will be included in the premanifest carrier group. Prospective data will be categorized at the end of the study into five groups: (1) premanifest carriers whose SARA total score remain in the 0-2.5 range; (2) mildly affected early-stage patients who had an initial SARA total score 3-9.5, which may increase in subsequent years; (3) premanifest participants who phenoconvert during the study period with a SARA total score increase from the 0-2.5 range to ≥ 3 ; (4) SCA1 and SCA3 patients who had a SARA total score <10 during the 2009-2012 CRC-SCA natural history study (or during the ESMI, SPATAX or EUROSCA studies) who may have higher SARA scores during this study; and (5) gene mutation negative controls. Their annual disease progression will be characterized by statistical analyses of annual changes of COA measures, with the SARA total score as the primary outcome measure.

Study duration: Five years

Recruitment of prospective study subjects:

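### Two of the five progression groups are formed at study end from follow-up SARA, the primary outcome, so their annual SARA change does not describe premanifest carriers as enrolled

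*Protocol*

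**What the plan says.** The Study population section under Prospective Data Collection states that "Prospective data will be categorized at the end of the study into five groups". The three groups that matter here are:

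- Group 1: "premanifest carriers whose SARA total score remain in the 0-2.5 range".
- Group 2: "mildly affected early-stage patients who had an initial SARA total score 3-9.5, which may increase in subsequent years".
- Group 3: "premanifest participants who phenoconvert during the study period with a SARA total score increase from the 0-2.5 range" to 3 or more.

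Group 4 is set by SARA in the earlier natural history studies and group 5 by genotype. The section continues: "Their annual disease progression will be characterized by statistical analyses of annual changes of COA measures". The same sentence makes the SARA total the primary outcome.

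So groups 2, 4 and 5 rest on information fixed before follow-up begins. Only the carriers who were premanifest at entry are divided by what their SARA does afterwards.

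Two other places bear on this. Aim 3 and Statistical Methods name mixed models, GEE, joint models, pattern-mixture models and latent class models. Neither says whether premanifest SARA change is estimated by baseline category or within the end-of-study groups. Table 3 plans 170 entrants in Year 1 and 38, 11, 10 and 9 in Years 2 to 5.

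**The concern.** The variable that assigns a carrier to group 1 or group 3 is the variable whose annual change is then reported for that group. Group 1 is selected for not having risen past 2.5 and group 3 for having done so. Upward rating error at follow-up helps move a carrier into group 3, and its absence helps keep a carrier in group 1. The two group means would therefore differ even if every carrier progressed at the same rate.

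The study's purpose is to prepare trials. A trial that recruits premanifest carriers cannot know at entry who will later cross a SARA of 3, so the rate it needs is that of all carriers as enrolled. Neither group supplies that rate. A planner who took the group 1 rate would expect too little progression; one who took the group 3 rate would expect too much.

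**Working it through.** The protocol states no SARA slope, SARA variance or power for Aim 1 (Sample Size Justification bases Aim 1 on feasibility), so there is no figure of its own to reproduce. The check has a part that follows from the definitions and a part that needs assumptions.

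**From the definitions.** A group 1 member scores between 0 and 2.5 at every visit. With a baseline and four annual follow-ups, the first-to-last change cannot exceed 2.5 / 4 = 0.625 points/year. A group 3 member must at some visit be at least 3 − 2.5 = 0.5 points above baseline. One group is capped above and the other has a required rise.

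**Simulation, with inputs that are assumptions and not in the protocol.** True entry SARA has mean 1.2 and SD 0.7. Observed scores are rounded to 0.5 and floored at 0, and a carrier enters if the observed score is 2.5 or less. There are four annual follow-ups. Rating-error SD is 0.7, with a range of 0.5 to 1.0. A least-squares slope is fitted per person. Group 3 is any follow-up score of 3 or more; group 1 is the rest. About 360 to 390 thousand carriers were retained per scenario.

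| True slope for every carrier (points/year) | Group 1 | Group 3 | All baseline-premanifest |
|---|---|---|---|
| 0.30 | 0.23 (0.18 to 0.26) | 0.38 (0.36 to 0.40) | 0.30 to 0.31 |

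In this scenario no one differs in true slope, so the whole gap comes from the grouping.

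**Other true slopes.** A second simulation drew true entry SARA uniformly from 0 to 2.5, with one common slope and error SD 0.5 to 1.0:

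| True slope | Group 1 | Group 3 |
|---|---|---|
| 0 | 0.00 | 0.07 to 0.12 |
| 0.2 | 0.18 down to 0.12 | 0.26 up to 0.31 |
| 0.4 | 0.35 down to 0.24 | 0.44 up to 0.49 |
| 0.6 | 0.48 down to 0.33 | 0.62 up to 0.65 |

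With no true progression the low bias in group 1 vanishes, because its baseline and follow-up readings are then all subject to the same cut at 2.5. The high bias in group 3 remains.

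**Slopes that differ between people.** With mean slope 0.4 and slope SD 0.3, group 1 shows 0.12 to 0.17 and group 3 shows 0.58. The members' own true slopes are 0.20 and 0.51 to 0.56. At error SD 0.5 the observed gap is 0.58 − 0.17 = 0.41 and the true gap 0.56 − 0.20 = 0.36. At error SD 1.0 they are 0.58 − 0.12 = 0.46 and 0.51 − 0.20 = 0.31. Artefact is thus 0.05 to 0.15 points/year of the gap, and the rest is real separation of slow from fast progressors. All baseline-premanifest carriers together show 0.41 to 0.42, close to the true 0.40.

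**Follow-up length.** Table 3 has 38 + 11 + 10 + 9 = 68 entrants after Year 1 (all categories). Year 1 entrants can have four follow-up visits, and Year 2, 3, 4 and 5 entrants three, two, one and none. With every carrier at 0.30 points/year and error SD 0.7, group 3 shows about 1.5 points/year after one follow-up and 0.38 after four. The same underlying progression therefore gives very different group 3 rates depending on when people joined.

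**The case against.** The strongest reply is that trial planning belongs to Aim 3, which speaks of progression in premanifest carriers and early-stage patients, not of the five groups. Aim 3 also refers to progression after onset in premanifest participants, which must include people who convert. Nothing says that its mixed, joint and latent class models are fitted separately within groups 1 and 3. This stands in part. A reader might infer that every premanifest progression estimate in the study is affected, and the protocol does not support that. But Aim 3 does not replace the grouping in the Study population section or say that premanifest SARA change is estimated by baseline category. That section does tie the primary outcome to the five groups. Mixed models fitted within groups 1 and 3 would inherit the selection.

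A reader might also infer that one SARA reading of 3 or more is enough to count as conversion. The protocol does not say so. The same section speaks of subjects becoming clinically ataxic, participant category is recorded at each follow-up visit (Table 4), and a confirmation rule is normal content for an analysis plan that is not at hand. In the first simulation with no true progression, 14% (7% to 26%) cross on a single reading and about 2% (1% to 4%) at two consecutive readings. The 14% is a false-conversion rate only if single readings count.

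It is also fair to say that describing stable carriers and converters separately is a legitimate aim, that this is an observational study with no test or decision resting on these two rates, and that baseline category and all SARA scores are kept, so the baseline-defined rate can always be computed. All of this limits the severity. It does not make either group rate a rate for carriers as enrolled.

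**Conclusion.** The point holds. Groups 1 and 3 condition on the primary outcome. Relative to carriers as enrolled, annual SARA change is biased low in group 1 and high in group 3, and the group 3 figure also shifts with length of follow-up.

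The direction follows from the definitions, except that the group 1 bias disappears if there is no true progression. The size rests on assumed slopes, entry scores and rating error. At 0.30 points/year for everyone, the group 1 shortfall is 0.04 to 0.12 (0.30 − 0.26 to 0.30 − 0.18) and the group 3 excess 0.06 to 0.10 (0.36 − 0.30 to 0.40 − 0.30). At a true 0.2 with error SD 0.5, the group 1 shortfall is only 0.02.

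It would be too strong to call the whole difference between the groups bias: if carriers progress at different rates, most of it can be real, as the mixed-slope scenario shows. The baseline-defined estimate is not perfect either. The entry cut and the floor at 0 push it up slightly, to 0.20 to 0.24 for a true 0.2. This should be fixed, but it is not a fatal fault.

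**What to change.** In the Study population section, define the primary SARA progression analysis by baseline category. All genotype-positive participants with baseline SARA 0 to 2.5 form one group, including carriers found among the 50%-at-risk subjects. Early-stage patients, previously early-stage patients and gene-negative controls are the others. The inclusion criteria table already holds the enrolment categories needed. Analyse phenoconversion as a time-to-event outcome, which also handles unequal follow-up, and label groups 1 and 3 as descriptive.

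As an optional sensitivity analysis, report how often gene-negative controls cross SARA 3, and how many carriers cross at two consecutive assessments.

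The cost is protocol wording and a little more analysis; no new data are needed. In the two-assessment sensitivity analysis, crossings at the last visit cannot be confirmed and stay provisional.

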We will enroll a subset of the prospectively enrolled 200 subjects in Aim 1. These subjects will consist of 30 (20 premanifest and 10 early-phase) subjects with the SCA1 mutation, 40 (27 premanifest and 13 early-phase) subjects with the SCA3 mutation and 30 controls (drawn from at-risk subjects who test negative for SCA1 or

SCA3 gene mutations and from spouses and other relatives who do not have symptoms, signs or risks of ataxia). We will enrich the SCA1 and SCA3 cohorts by inviting participants with a predicted time to ataxia onset within 10 years, based on their CAG repeat length and current age. For premanifest carriers and participants who are 50%-at-risk, we will target an age range of 27-50 years to minimize the probability of including participants too far from disease onset and those who are highly unlikely to have an expansion of CAG repeats in SCA1 or SCA3.

Study duration:

Participants will be scanned (within ± 2 weeks of the clinical study visit) at baseline, 6 month, 12 month, 24 month and 36 month time points during the READISCA study period. All MR visits will include completion of SARA exam prior to MR scan. Three additional time points may be included in the MR sub study to incorporate scans at 6 months, 18 months and 36 months.

Inclusion and exclusion criteria:

Inclusion criteria for Aim 2 will be the same as those in **Aim 1** and willingness to undergo MR procedures.

Exclusion criteria for Aim 2 will be the same as those in **Aim 1** and inability to undergo MRI scanning (claustrophobia, presence of paramagnetic substances or pacemakers in body, weight over 300 lbs.), pregnancy or lactation in women of childbearing potential not protected by an effective means of contraception, and other neurological diseases than those of interest. In addition, potential study participants will be excluded from the study if any of the following criteria are present at any point in the study: structural abnormalities such as subdural hematoma, primary or metastatic intracranial neoplasms, and concurrent illnesses or treatments interfering with cognitive function, such as a stroke or normal pressure hydrocephalus.

Table 4. Study visits	Screening visit (Likely same day as baseline)	Baseline visit	Year 2 follow up visit	Year 3 follow up visit	Year 4 follow up visit	Year 5 follow up visit
COVID-19 Questionnaire	✓		✓	✓	✓	✓
Eligibility	✓					
Demographic data	✓					
Age at onset	✓					
Therapy review	✓		✓	✓	✓	✓
Complete History ¹	✓					
Interval History ²			✓	✓	✓	✓
General physical assessment	✓					
Prior DNA result check (if available)	✓					
Baseline DNA result check ³			✓			
Concomitant medications	✓		✓	✓	✓	✓
SARA ⁴	✓		✓	✓	✓	✓
Plasma		✓	✓	✓	✓	✓
Whole blood (PBMCs)		✓				
9HPT, T25FW, Click Test		✓	✓	✓	✓	✓
CCAS		✓	✓	✓	✓	✓
INAS, Functional stage		✓	✓	✓	✓	✓
Patient Global Impression, EQ-5D, PHQ9, FA-ADL, Fatigue Severity Scale		✓	✓	✓	✓	✓
Category of participant			✓	✓	✓	✓
MRI/MRS/fMRI ⁵		✓	✓	✓	✓	✓
Blood sampling ⁶	✓	✓				
CSF sampling (optional) ⁷		✓	✓	✓	✓	✓
AE/SAE review		✓	✓	✓	✓	✓
Conclusion of study participation						✓

¹Complete history include general medical history. ² Interval history will include general medical history, age at onset and therapy review. ³The result of baseline DNA testing will be checked as soon as it becomes available before the Year 2 follow up visit. ⁴ SARA will be done for assessment of inclusion criteria at the screening visit, but it will not be repeated at the baseline visit if both visits occur on the same day. SARA may also be re-evaluated at imaging site prior to each scan. All SARA assessments will be videotaped following recommended guidelines. ⁵MRI/MRS/fMRI will be performed at specified timepoints for three consecutive years. Therefore, the first MRI/MRS/fMRI study may be performed in the first, second, or third year. Additional scanning may be obtained at 6 months, 18 months and 36 months. ⁶ DNA samples will be collected at screening or baseline visit. An additional DNA sample may be collected to confirm results of genetic testing for 50%-at-risk participants. ⁷ CSF samples may be collected up to 2 times. Additional DNA sample will be collected during either the first or second LP procedure.

Aim 3. Adapt recent developments on statistical design and analysis of small population trials to SCAs.

We will confirm the disease progression rate for the clinical outcomes and MRI and MRS biomarkers in premanifest carriers and early-stage patients. Linearity of evolution of clinical outcomes will be confirmed in early-stage diseases. We will examine whether expected linearity of the disease progression on MRI and MRS measures correlates with disease progression on COA measures after the disease onset in premanifest participants. Mixed models and joint mixed models will be used in order to establish the joint evolution of clinical and MR biomarkers and to define a threshold for non-linear evolution. The effect sizes for each COA and MR biomarker will be calculated and the MR biomarker(s) most sensitive to premanifest disease will be identified. We will also confirm that the CAG repeat size is a genetic modifier that can be used to predict the age of ataxia onset, using mixed models incorporating the predictors via interactions. We will also define

subgroups with different evolution to optimize the statistical power of future trials by lowering all sources of variability. For this purpose, trajectory models such as Latent Class Mixed Model will be implemented both on baseline severity data and disease evolution. For simulations, we will test following strategies: (1) using external control data including historical controls, (2) using relaxed statistical error rates, (3) optimizing the design using “umbrella trial,” group sequential design, crossover, n-of-one, and re-randomization designs, and (4) using repeated measures.

Adverse Events/Serious Adverse Events

Serious adverse events are defined as any untoward medical occurrence during the study period

- results in death,
- is life-threatening
- requires inpatient hospitalization or causes prolongation of existing hospitalization
- results in persistent or significant disability/incapacity,
- is a congenital anomaly/birth defect, or
- Requires intervention to prevent permanent impairment or damage.

The term "life-threatening" in the definition of "serious" refers to an event in which the patient was at risk of death at the time of the event; it does not refer to an event which hypothetically might have caused death if it were more severe.

Adverse events are further defined as “Any untoward medical occurrence in a patient or clinical investigation subject administered a pharmaceutical product or exposed to a research related environment and which does not necessarily have to have a causal relationship with this treatment.

All adverse events, including those associated with MRI/MRS procedures, will be reported to the Steering Committee via the HMRICC, which will coordinate necessary measures to address medical needs that resulted from the adverse event. Serious adverse events will be reported within 24 hours to the HMRICC, officials at the NIH, and the IRB. HMRICC will immediately notify the Steering Committee members. The Steering Committee will act to address the problem and implement measures to prevent similar problems. The Steering Committee will also report all adverse events to the *Data and Safety Monitoring Committee*.

Potential Risks

An assessment of potential risks for this project includes the following:

- **Risk of loss of confidentiality**: Participants will be asked to provide medical information documenting their condition for this research project. Such information will be stored in a secured access database at the site where the participant is enrolled in the study. Only research personnel working on this READISCA project at that site will have access to the data. If results of the study are published, the identity of participants will not be disclosed. Data and biological materials obtained from participants will be de-identified before they are sent to other sites for analysis and storage. The newly assigned code to de-identify the data can be linked to the participant’s PHI only by the site investigator and coordinator who enrolled or examined the participant. Any information, which link the de-identified data to PHI, will be kept in either a locked cabinet or a password-protected computer file, which only the site investigator and coordinator can access. All PHI will be protected by the Health Insurance Portability and Accountability Act (HIPAA) and the Genetic Information Nondiscrimination Act (GINA) in the US and equivalent laws in Europe.
- **Risk of falls and resultant injuries during neurological evaluations**: While the risk is minimal, participants may have balance problems and may fall during study visits.
- **Risks and/or complications of optional spinal tap**: Risks of a lumbar puncture (LP) procedure, include (maximal complications in parentheses) local pain and irritation at the site of needle injection, a 5% to 30% risk of post-LP headache, and less than 1% risk of infection (meningitis), avulsion of nerve root (focal neurological deficit), bleeding into spinal canal (cauda equina syndrome with paralysis of legs), and extremely rare brain herniation syndromes (death). If a participant develops a headache in upright posture that significantly improves by lying down, but does not improve after 12 hours of bed rest, fluids, or ibuprofen/Tylenol®, a blood patch may be necessary.

- Risks associated with venipuncture: Venipuncture may cause local subcutaneous bleeding or puncture site infection. Some individuals may have vagal syncope, which may result in fainting.
- Risk of claustrophobia: Some individuals may become claustrophobic during MR testing and if this occurs, the scan will be discontinued immediately.
- Risks associated with the 3T scanners: The FDA has classified these systems as devices of non-significant risk and serious risks are not expected. However, some participants may experience minor dizziness when moving in and out of the system, headache, flashing light sensation, or a metallic taste. Should participants experience any of these effects and wish to discontinue the study, they will be taken out of the scanners. These symptoms should resolve after the scan is discontinued. The only significant risk associated with utilizing high magnetic field strength magnets is that if highly magnetic materials are brought into the room containing the high magnetic field strength scanner, they will become projectiles and can cause injuries. To date, there have been no serious and/or permanent adverse effects associated with our 3T scanners. The participants are therefore at low risk during the study. At our centers, we have many IRB-approved protocols that involve 3T scans of various patient populations, including neurodegenerative diseases.

The alternative to participating in this project is to decline. Participants will be at no risk if they decline to participate.

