At any time during the study, the participant may revoke authorization to use data and/or samples. However, the sponsor and the study investigator can still keep and use any information that is already received to the extent necessary to preserve the integrity of the research study.

Sample Size Justification

For Aim 1 study of prospective data collection the sample size is guided by feasibility (regarding our realistic ability to enroll premanifest and very early stage subjects across US and Europe), rather than power. The sample size of 200 participants will ensure enrollment of >60 participants with SCA1 and >100 participants with SCA3, which should provide sufficient power at least equivalent to the previous US and EUROSCA studies.

For Aim 2 the sample size is determined based on the RISCA study, which included imaging data from 26 SCA1 mutation carriers and 9 SCA3 mutation carriers and reported significant VBM alterations in SCA1 and trends in SCA3. Based on these data, a Wilcoxon rank sum test will have 95% power to show a difference between controls (mean=0.018, SD=0.019) and SCA (mean= 0.016, SD=0.0019) with 30 subjects per group ($\alpha=0.025$ to take into account the two comparisons of SCA1 and SCA3 versus controls, two-tailed test). Note that this power computation is conservative since the RISCA study included only at-risk subjects, whereas the current study will include both premanifest and early manifest participants. In addition, based on our MRS preliminary data, a Wilcoxon-Mann-Whitney test will have 94% power to show a difference in NAA at baseline between premanifest subjects who have disease onset within the 5 years of the READISCA (conservatively estimated at 1/3 of the participants i.e. $n=7$, mean = 1.2) and those participants who remain in the premanifest stage ($n=14$, mean = 2) for the SCA1 group (standard deviation of 0.4, $\alpha=0.05$, two-tailed test). We will recruit a larger sample size for the SCA3 cohort because: 1) imaging alterations did not reach significance for SCA3 mutation carriers in the RISCA study; 2) the diffusion MRI abnormalities were less pronounced in SCA3 than those in SCA1; and 3) SCA3 is the most common SCA, enabling recruitment of a larger cohort.

Statistical Methods

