For Aim 2 centralized data analysis will be performed. De-identified MRI and MRS data will be analyzed in a blind fashion at UMN, as described previously for volumetric, VBM and MRS analyses. Diffusion MRI data will be analyzed using tract-based spatial statistics (TBSS), which is part of the FMRIB’s Software Library (FSL), and tractography to delineate particular white matter (WM) pathways (e.g., cerebellar peduncles). Functional (rs fMRI) data will be pre-processed using FSL, followed by between-group analyses using seed-based connectivity analysis for particular regions of interest, and independent component analysis/dual regression (MELODIC/FIX) for resting-state networks (RSNs). Normative data from the Human Connectome Lifespan project will supplement matched-control data acquired prospectively. Outcome measures will consist of cerebellar and brainstem volumes, gray matter (GM), and WM loss metrics from VBM, metabolite concentrations, fractional anisotropy, mean diffusivity, radial and axial diffusivity, as well as degree of co-activation within RSNs of interest (e.g., motor function). These multi-modal imaging data will then be incorporated in the predictive model to stratify future clinical trial cohorts in Aim 3.

To compare the imaging biomarkers between SCA1, SCA3 and control cohorts, globally and in a pairwise fashion, we will use Wilcoxon rank sum test. In addition, premanifest carriers and early-stage participants will be compared using Wilcoxon rank sum test. Within each SCA group, premanifest and manifest patients will be compared regarding the biomarkers at baseline and during follow-up. If this approach is not conclusive, cluster approaches will be carried out. Sex will be considered as a biological variable to assess potential sex-based differences in imaging results. Finally, the MR biomarkers will be included in the predictive model (Aim 3).

Ethical Conduct of the Study:

This study will be conducted with the highest respect for the individual participants (i.e., subjects) according to the protocol, the ethical principles that have their origin in the Declaration of Helsinki (18th World Medical Assembly, 1964) and its last revision (Fortaleza, October 2013) (48), the ICH Harmonized Tripartite Guideline for GCP and local laws and regulations of the country where the study is performed.

Clinical Trial Registration:

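### The most sensitive MR biomarker is chosen, and its effect size estimated, in the same 20 to 27 premanifest carriers per genotype, so the reported effect will on average be too large

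*Protocol*

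**What the plan says.** The selection rule is in the Aim 3 paragraph of the protocol: an effect size is computed for every clinical outcome and every MR marker, and "the MR biomarker(s) most sensitive to premanifest disease will be identified". The same paragraph then turns to the power of later trials and lists design strategies to be simulated. It does not say which effect sizes those simulations will use.

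The candidates are listed for Aim 2 under Statistical Methods: "Outcome measures will consist of cerebellar and brainstem volumes, gray matter (GM), and WM loss metrics from VBM, metabolite concentrations, fractional anisotropy", followed by three more diffusion metrics and resting-state network co-activation. Counted as families these are:

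- cerebellar volume and brainstem volume
- grey-matter loss and white-matter loss
- metabolites
- four diffusion metrics
- network co-activation

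That makes ten, before any split by region, tract or metabolite.

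The sample is in the Aim 2 study population section: "30 (20 premanifest and 10 early-phase) subjects with the SCA1 mutation" and "40 (27 premanifest and 13 early-phase) subjects with the SCA3 mutation and 30 controls". The only outside imaging data named are normative controls. The list of aims nevertheless presents Aim 2 as validating the MR biomarkers.

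After the Aim 2 group comparisons, Statistical Methods adds: "If this approach is not conclusive, cluster approaches will be carried out".

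**The concern.** Calculating an effect for each of many markers, taking the largest and reporting that value uses the data twice. The winner is partly the best marker and partly the luckiest one. With 20 or 27 carriers, a standardized difference has sampling error that is large compared with plausible gaps between markers, so luck carries weight.

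The study exists to prepare trials in a rare disease with few premanifest carriers. A selected marker with an inflated effect is the kind of result that later trial planners would take up, and an underpowered trial in this population is hard to repeat. Calling the exercise validation makes it more likely that the value is taken at face value. A second, results-triggered attempt by clustering adds another unplanned route to a positive finding.

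**Working it through.** **Is there a figure to reproduce?** No. The protocol gives no effect for a selected marker and sizes no future trial. What follows is an illustration under stated assumptions.

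**Inputs from the protocol.** 20 or 27 premanifest carriers, 30 controls, at least 10 families of measures.

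**Assumed inputs.** True standardized effect d, correlation rho between markers, number of markers K, and a future trial with 80% power, two-sided alpha 0.05 and a treatment that removes half of d.

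**Method.** Simulate K correlated markers in carriers and controls (4,000 runs), compute each observed d and keep the largest. Sample size varies as 1/d², so the shortfall factor is (mean selected d ÷ true d of the selected marker)². The assumed treatment fraction cancels out of this factor.

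**Check without selection.** One pre-chosen marker, 27 carriers, true d 0.8: mean observed d 0.81, 95 per arm planned against 99 needed, real power 79%. The method itself adds almost no bias.

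**Worked example.** Ten equal markers, rho 0.5, 20 carriers, true d 0.8. Mean selected d is 1.17, an inflation of 1.46.

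- Needed: d × 0.5 = 0.40, so n = 2 × (1.96 + 0.84)² ÷ 0.40² ≈ 98, or 99 per arm with the t correction.
- Planned: 1.17 × 0.5 = 0.585, so n ≈ 2 × 7.85 ÷ 0.342 ≈ 46, or 47 with the t correction.
- Real power with 47 per arm is 49%, not 80%. The shortfall is 99 ÷ 47 ≈ 2.1.

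**Near worst case.** K = 10 to 20, all with true d 0.5, rho 0.2 to 0.5. Mean selected d is 0.82 to 1.03.

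- (0.82 ÷ 0.5)² ≈ 2.7
- (1.03 ÷ 0.5)² ≈ 4.2

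**One marker truly better** (10 markers, rho 0.5):

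| Best v rest | Carriers | Selected d ÷ its true d | Factor | Right marker chosen |
|---|---|---|---|---|
| 0.8 v 0.5 | 20 | 1.44 | 2.1 | 46% |
| 0.8 v 0.5 | 27 | 1.38 | 1.9 | 51% |
| 0.8 v 0.2 | 20 | 1.15 | 1.3 | 87% |
| 0.8 v 0.2 | 27 | 1.10 | 1.2 | 91% |

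**Other spreads.** True effects spaced evenly from 0.2 to 0.8, rho 0.2 to 0.8, gave factors of 1.4 to 2.8. One marker at 1.05 and nine at 0.4 gave 1.1 to 1.5.

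**Change over time instead of carriers against controls.** Ten equal markers, rho 0.5, 20 carriers, true standardized change 0.8: mean selected 1.19, inflation 1.49. The bias does not depend on the cross-sectional set-up.

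**Does the remedy work?** In each bootstrap resample, select again, take the winner's d in the resample minus the same marker's d in the full sample, average these differences and subtract the average from the observed maximum. With 20 carriers, 10 markers and rho 0.2:

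- Equal markers at 0.50: 0.94 falls to 0.61, removing 0.33 of a bias of 0.44.
- Markers spread from 0 to 1.05: 1.22 falls to 0.95 against a true 0.93, removing 0.27 of 0.29.

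**The case against.** **The link to trial planning is not written down.** A reader might infer from the order of sentences that the selected marker's effect feeds the simulations and that future trials will therefore be too small. The protocol does not say so. The uses it does state for MR data in Aim 3 are joint models of progression and a model for stratifying later cohorts. The simulations could instead rest on clinical outcomes from the 200-subject cohort, where SARA is primary. This stands, so the consequence for trial size is conditional. The bias in the reported effect of the selected marker is not.

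**The largest factors need equal markers.** Equality leaves selection nothing real to find. The only volumetric figures in the Sample Size Justification imply d = (0.018 − 0.016) ÷ 0.0019 ≈ 1.05, if the control SD of 0.019 is a misprint for 0.0019. With all markers at 1.05 the factor is 1.8 to 2.4. This also stands, and 2.7 to 4.2 should be read as an upper region.

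**Much of this could be settled in an SAP that is not shown.** That is true of multiplicity rules, and a Holm correction across all markers is not pressed here. But the protocol itself fixes a select-the-largest rule and a validation label, and both can be judged as written.

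**The alpha of 0.025.** A reader might take it as an inadequate adjustment for the whole marker list, and compute 1 − 0.975¹⁰ = 22% to 1 − 0.975²⁰ = 40% for at least one false positive. The text says only that it is "to take into account the two comparisons of SCA1 and SCA3 versus controls", in a power calculation for one measure, which is an accurate description. The 22 to 40% also assumes independent markers with no true effects. No fault is found there.

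**Conclusion.** The plan as written selects a marker on its observed effect among at least ten families of measures, in 20 or 27 premanifest carriers, and names no independent carriers in whom to confirm it. The selected effect is biased upward on average. In a single study it may still fall below the truth: this happened in 0 to 28% of runs with 5 to 20 equal markers.

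If that uncorrected effect informs the Aim 3 simulations, sample sizes will tend to be too small. The factor is about 1.2 to 2.1 when one of ten markers at correlation 0.5 is truly better, somewhat wider under other spreads (1.1 to 2.8), and about 2.7 to 4.2 for 10 to 20 equal markers at d 0.5. Effect sizes, correlations and marker counts are all assumed. The direction was the same in every scenario, but the size is not known. The change is worth making, and the protocol is not shown to lead to an undersized trial.

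**What to change.** In the Aim 3 paragraph, state that:

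1. the selection step is repeated on the derived biomarker measures within each bootstrap resample;
2. optimism-corrected effect sizes with intervals are reported for the selected marker or markers;
3. any Aim 3 simulation that uses an MR effect size uses the corrected value with its uncertainty, including the lower limit as a scenario.

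In the Aim 2 part of Statistical Methods, label the cluster fallback exploratory.

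The cost is some extra analysis and smaller reported effects. No participants or scans are added. Working on derived measures avoids re-running the image-processing pipelines in each resample, but regions and tracts should then be fixed beforehand, because the bootstrap cannot correct for choices made upstream of it. With 20 to 27 carriers the lower limit may lie near zero. That would be a fair statement of what the data can support.
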